The key physiologic principle that drives weaning from mechanical ventilation surrounds effort of breathing. The clinical surrogates for effort of breathing are based on clinical examination, are subjective, and have high inter-rater variability. Direct measurement of effort of breathing is possible using minimally invasive techniques with naso-esophageal tubes, spiroometers, and respiratory inductance plethysmography (RIP) bands. We have strong preliminary data from a completed NIH funded investigation here at CHLA (CCI-11-00210) involving > 400 mechanically ventilated children (neonates to adolescent) that objective measures of effort of breathing may aid clinical decision making regarding readiness for extubation, detecting and managing complications after extubation such as upper airway obstruction (UAO), and titrating noninvasive ventilation support. We have recently applied for RO1 award to conduct a follow up study which would be a randomized controlled trial comparing an objective measure of effort of breathing (esophageal manometry) guided approach to a more conventional ventilator protocol, incorporating current evidence. Our hypothesis is that this protocol will lead to faster ventilator weaning, by preserving diaphragm and other respiratory muscle strength. To do this, we plan to incorporate physiologic measurements and calculations which will be displayed as part of a software program we have developed, provide recommendations to the clinicians who will ultimately accept or reject the protocol recommendations, and provide feedback as to why

they rejected the recommendations. This pilot study will help test the acceptability of our study protocols with bedside providers, , ensure the user interfaces and recommendations are easy to follow, demonstrate the feasibility of performing repeated diaphragm ultrasound measurements, and help determine the potential effect size of the intervention to determine ultimate sample size calculations.

2. Background literature

Typical Course of Mechanical Ventilation

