Preliminary Data from CHLA (published): We have previously demonstrated using data from our own institution, that clinicians frequently do not follow evidence based guidelines regarding ventilator management, and there are potentially lost opportunities to improve our ventilator management by complying with current best evidence[17]. These protocols will form the basis for ventilator management as part of this study, and effort of breathing calculations will be added on top of these existing guidelines. The suite of software tools simply gather data from the available clinical data at the bedside (laboratory feeds, ventilator connections), determine what the current best-evidence would suggest be done for the patient based on these parameters, and make a recommendation to the clinician. Ultimately, the clinician will determine whether to accept or reject the recommendation, and provide an explanation for why the recommendation was rejected to eventually improve the adherence to the protocol.

Transpulmonary pressure

While implementing current evidence based guidelines has the potential to reduce length of mechanical ventilation and minimize risk of ventilator induced lung injury, there is the potential to improve on the current best evidence through optimization of ventilator support during the acute phase of illness. Transpulmonary pressure based titration of ventilator settings has demonstrated utility in the management of adult patients with ARDS to improve oxygenation [18]. *Preliminary Data from CHLA (unpublished):* We have preliminary data here as part of another approved study (CCI-13-00370) that there may be differences between clinician chosen ventilator settings, and recommendations based on transpulmonary pressure. However, what is unclear and impossible to ascertain with the previous study design, is whether there would be a

difference between ventilator settings recommended by Trans-Pulmonary Pressure (with the use of esophageal manometry), and the current best evidence based guidelines. Our preliminary data demonstrates that TPP measurements are simple to obtain, may be different than clinically chosen values for, in particular, Positive End Expiratory Pressure (PEEP), and that changing PEEP values to normalize TPP is safe, with no significant change in cardiac output or oxygen delivery.

Upper Airway Obstruction

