not tracked, as that was not the intention of the study. Nor were there any specific protocol recommendations for management based on the calculations in the tool. For this proposed study, the clinicians would have ready access to the tool for assistance with clinical decision making regarding weaning, and post-extubation management. Based on effort of breathing calculations within the tool, there will be specific recommendations regarding weaning or no weaning. The effort of breathing guided protocol rules will be incorporated in the CDS tool above and ultimately the clinician will decide whether or not to wean by evaluating the patient, and knowing the effort of breathing trend since the last evaluation. If the clinician elects not to wean when the protocol recommends a wean, they will record why using the tool above.

3. Purpose of this study

Study Objectives

1. To refine the esophageal manometry based effort of breathing weaning protocol so that it can be used easily, and can attain high protocol adherence for eventual use in a randomized controlled trial.
2. To demonstrate that integration of these two pieces of software together can be used safely to provide recommendations for ventilator management, and measure protocol adherence.
3. To determine the potential magnitude of reduction in length of mechanical ventilation afforded by using such a weaning tool, to help determine estimated sample size for a future randomized controlled trial.
4. To obtain data regarding the potential difference between Transpulmonary pressure guided PEEP management and management recommended by current best evidence using a PEEP/FiO₂ titration table, for eventual use in a clinical trial.
5. To refine the esophageal manometry based effort of breathing protocol for weaning non-invasive ventilation after extubation.
6. To determine the feasibility and reproducibility of diaphragm ultrasound measurements amongst providers.

4. Research Design and Methods

Study Overview

Effort of breathing guided ventilator management for children: a pilot study

Protocol Version Date: March 2, 2021

This is a single center prospective trial in the 24 bed multidisciplinary medical-surgical pediatric intensive care unit (PICU) at Children's Hospital Los Angeles. All patients intubated and mechanically ventilated with an anticipated length of intubation > 48 hours will be eligible. Specific inclusion and exclusion criteria are delineated below.

5. Eligibility and Recruitment

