The endpoints of the study for individual patients will occur 48 hours after extubation. . The bands and esophageal catheter will be removed 1 hour after extubation for study purposes. However, if the clinical team would like to use the catheter or bands for ongoing patient management, it can be left in place but will no longer be considered a study specific intervention. The patient will be followed for 48 hours to track therapies and re-intubation.

7. Analysis and Sample Size

In performing sample size calculations for the eventual proposed RCT, with an anticipated 1 day reduction in effort of breathing between intervention and control groups, the expected number of patients will range from 300-700 patients per arm. For this reason, the eventual study would need several years to complete, or be performed as a multi-center RCT. Estimates of treatment effect generated from this study will help refine these estimates.

For this pilot study, the requested sample size is 40. The sample size has been increased from the initial 20 to 40 to accommodate the changes in the CDS tool platform, the protocol changes to the effort of breathing algorithm, and the diaphragm ultrasound measurements. We believe this sample size is necessary to test all of the stated objectives. By objective

1. Refining esophageal manometry protocol: It is anticipated that 40% of patients will pass the initial SBT. This means that 10-12 patients will be left to test the protocol. Each patient should generate 10-20 recommendations on the weaning protocol, giving approximately 100 recommendations to test. Based on preliminary analysis of the 20

included patients to date, and in discussions with the bedside providers, we have modified the esophageal manometry protocol to allow for 3 ranges of adjustment, rather than 2. It is believed that this will improve adherence, while still meeting the physiologic principles of titration of ventilator support to maintain effort of breathing. The subsequent 20 patients would then be used to test if the revised protocol attains high adherence.

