2. Software pieces: Each patient should receive at least 24 recommendations on the CDS portion of the protocol and for those that fail the SBT, another 10-20 recommendations on the weaning protocol. We have migrated the CDS tool out of Microsoft Access, making it available in a web-browser to improve compatibility with clinical care. The rules of the protocol have not changed. The additional analysis will be to confirm that users can follow the new user interface. This should afford enough data to test the reliability of the software. From the 10-12 patients who are enrolled in the weaning protocol, at least 2 time points will be available to compare PRP values between the software tool and the post-processing program, allowing > 20 points for direct comparison.
3. Magnitude of reduction: It is anticipated that the expected duration of MV for those with anticipated lengths > 48 hours ranges from 5-7 days on average, with a wide range. While it is unlikely that we will have a definitive answer about the magnitude of effect, approximately 20 patients should provide data to get a reliable estimate of mean and standard deviation for length of ventilation to use in future calculations.
4. TPP separation: It is anticipated that 20 patients should yield a minimum of 60 TPP measurements (average 3/patient) which can be used to identify a potential separation between PEEP recommended by the protocol, and that which would be recommended by normalizing TPP. From the preliminary data we have to date (approximately 9 patients), there appears to be an average separation of 2 cmH₂O between clinician chosen PEEP and PEEP at TPP, although the variation is large. However, most of the time clinician chosen PEEP is below the evidence based recommendations. If we can demonstrate that for at least 50% of the observations (95% Confidence Interval 40-60%) there would be a separation of at least 2 cmH₂O, it would facilitate development of a protocol. To achieve this level of confidence, we would need a minimum of 50 observations.
5. NIV protocol: It is anticipated that 40% of patients who are extubated will be placed on NIV after extubation. This means that 10-12 patients will be left to test the protocol. Each patient should generate 10-20 recommendations on the NIV weaning protocol, giving approximately 100 recommendations to test.

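### The pilot promises estimates of treatment effect on ventilation time but has one arm and no comparator, and its fallback standard deviation is called reliable with no interval

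*Combined protocol and SAP*

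**What the plan says.** Section 7 (Analysis and Sample Size) gives the RCT assumption as "with an anticipated 1 day reduction in effort of breathing between intervention and control groups, the expected number of patients will range from 300-700" patients in each arm, and adds: "Estimates of treatment effect generated from this study will help refine these estimates". Objective 3 in section 3, repeated under Study Outcomes, is to find how large a reduction in ventilation time the tool might bring. The primary outcome for it is invasive plus non-invasive ventilation time. The opening section likewise expects a potential effect size from the pilot.

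Under Study Treatments, the CDS tool goes to every enrolled patient. All who meet the spontaneous-breathing criteria enter the effort-of-breathing weaning arm, which is a phase of care and not an allocated group.

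Item 3 of section 7 says that "the expected duration of MV for those with anticipated lengths > 48 hours ranges from 5-7 days on average, with a wide range". It concedes: "While it is unlikely that we will have a definitive answer about the magnitude of effect". It then claims that "approximately 20 patients should provide data to get a reliable estimate of mean and standard deviation for length of ventilation". The sample is now 40, raised from 20, and the weaning algorithm was changed after the first 20 patients.

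The opening section describes the RCT as comparing an esophageal-manometry "guided approach to a more conventional ventilator protocol, incorporating current evidence".

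**The concern.** A reduction is a difference between two quantities, and this design produces one of them. More patients would tighten the estimate of ventilation time under the protocol but would never supply a control value. Any reduction reported from the pilot would depend mainly on the benchmark chosen afterwards. If that figure fed the RCT, a trial of 600-1,400 children (300-700 per arm, two arms) could be sized on the wrong contrast. What the pilot can legitimately supply is the variability of ventilation time. RCT size is proportional to SD squared, so the precision of that SD matters, and the plan does not state it.

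**Working it through.** **1. Is there a comparator?** The text describes no randomisation, concurrent control or historical cohort for ventilation time. The earlier institutional cohort is used to set the pressure-rate product targets and to check the software, not as a ventilation-time control.

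**2. Could the 5-7 day figure serve?** There are three obstacles.

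- *Width.* It has no source, cohort or SD. Its width is 7 − 5 = 2 days, against an assumed effect of 1 day. For a pilot mean of 5.5 days, the reduction is 5 − 5.5 = −0.5 day or 7 − 5.5 = +1.5 days.
- *Outcome.* It is for mechanical ventilation, without saying whether non-invasive time counts. The primary outcome includes it.
- *Contrast.* The RCT control is a conventional protocol that incorporates current evidence. The background section (Evidence based protocols) reports that "clinicians frequently do not follow evidence based guidelines regarding ventilator management". If 5-7 days reflects usual care, the difference would credit the CDS tool's effect to effort-of-breathing weaning.

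The earlier cohort would not isolate the RCT contrast either. Its clinicians could see the effort-of-breathing display, but "Nor were there any specific protocol recommendations for management based on the calculations in the tool".

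**3. The SD implied by 300-700 per arm.** The plan gives no SD, alpha or power, so its figure cannot be reproduced, only inverted. Assumptions: comparison of two means, two-sided 5%, and the 1 day read as a day of ventilation.

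SD = √[N / (2(z_α + z_β)²)] × 1 day

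| Power | N = 300 | N = 700 |
|---|---|---|
| 80% | 4.37 days | 6.68 days |
| 90% | 3.78 days | 5.77 days |

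These SDs are plausible, so 300-700 is not shown to be wrong.

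**4. Precision of the pilot mean.** The half-width is t(0.975, n−1) × SD/√n. Over SD 3.78-6.68 days it is 1.8-3.1 days at n=20 and 1.2-2.1 days at n=40. Even an exactly known benchmark would not resolve 1 day.

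**5. Precision of the SD under normality.** The limits are √[(n−1)/χ²] times the estimate. Squaring them gives the multiplier on RCT size.

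| n | SD multiplier | RCT size multiplier | Ratio of limits |
|---|---|---|---|
| 20 | 0.76-1.46 | 0.58-2.13 | 3.7 |
| 40 | 0.82-1.28 | 0.67-1.65 | 2.5 |

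The plan's range is 700/300 = 2.3-fold. For example, an observed SD of 4.37 days (300 per arm at 80% power) is compatible with 174-640 per arm at n=20 and 202-495 at n=40.

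**6. Skew.** The implied coefficient of variation (CV) runs from 3.78/7 = 0.54 to 6.68/5 = 1.34. A normal distribution would then put Φ(−1/CV) = 3% to 23% of durations below zero, so normality is doubtful. Simulated coverage of the nominal 95% chi-square interval for the raw SD, if durations are log-normal (400,000 samples per setting):

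| CV | n = 20 | n = 40 |
|---|---|---|
| 0.54 | 78% | 74% |
| 0.7 | 69% | 65% |
| 1.0 | 55% | 50% |
| 1.34 | 43% | 38% |

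The same interval for the SD of log duration keeps 95% coverage throughout. Converted to RCT size with the mean held fixed, it spans 4.6- to 9.8-fold at n=20 and 2.8- to 4.5-fold at n=40 over that CV range. The intervals in step 5 are therefore, if anything, optimistic.

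**The case against.** The strongest reply is that the plan already knows its limits. The section 7 sentence is a general lead-in that promises only help, the objectives speak of a potential effect, and item 3 doubts a definitive answer and falls back on a mean and SD. Nowhere does the plan propose to subtract the pilot mean from 5-7 days. The SDs and CVs above are back-solved from assumed alpha and power, and the CV uses a 5-7 day mean that may not measure the primary outcome. The 300-700 range is a planning range of unstated origin, not a sampling interval, so setting 2.5-fold against 2.3-fold is only a rough comparison.

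Much of this is fair. It shows that the remedy is rewording, and that the skew figures are illustrations. It does not remove the point. The hedge concerns imprecision, whereas the missing element is a control value, and the section 7 sentence carries no qualification. The 5-7 day figure is examined because it is the only reference value available to a reader who wants a reduction. Nor is asking for an interval foreign to the plan: item 4 of the same section states one for its own target.

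One further caution stands. Follow-up ends 48 hours after extubation, which may cut off non-invasive time and so affect the mean and SD themselves.

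**Conclusion.** The concern holds. As written, section 7 claims an output that the design cannot deliver. This conclusion needs no numerical assumption; it rests on the text's description of a single pathway (Figure 1 is not reproduced in the copy reviewed). The choice of benchmark alone can move a reported reduction by 2 days, twice the effect of interest.

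The SD remains useful for planning, but 20 or 40 patients cannot by themselves be relied on to narrow 300-700 per arm. The SD factors assume normality. The half-widths also rest on the assumed two-sided 5% and 80-90% power, and the coverage figures on log-normal durations as well. The correction should be made because it changes what the pilot may conclude and what feeds the RCT. It does not call the pilot's other objectives into question.

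**What to change.** 1. Restate objective 3 (section 3 and Study Outcomes), the effect-size wording in the opening section and the section 7 sentence. The aim becomes the distribution (mean, median, SD) of ventilation time under the protocol, and what informs the RCT is variability, not treatment effect. If a reduction is still to be reported, name and source one historical comparator with the same eligibility and outcome definition. Label the result an uncontrolled comparison that includes the CDS tool's effect, and do not use it as the RCT effect size.
2. In item 3, say whether the estimate uses 20 patients on one algorithm version or all 40, and name in advance which one feeds the RCT. Replace the claim of reliability with the expected precision. Report the SD of log duration with its chi-square interval (valid if durations are log-normal) beside the raw SD, overall and by algorithm version.
3. State that the pilot SD will enter RCT sizing with its uncertainty, and that the effect size will come from a stated clinically relevant difference. Leave the sizing rule to the RCT protocol.

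The cost is rewording and one small extra summary, with no new patients or measurements; the pilot's stated value becomes more modest. Only the historical-comparator option adds work: chart data on ventilation time for a matched earlier cohort.

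### Section 7 sets the sample at 40 but still justifies ventilation length and TPP on 20 patients, and 50 to 60 TPP observations do not give the stated 40-60% interval

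*Combined protocol and SAP*

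**What the plan says.** Section 7 (Analysis and Sample Size) of the combined protocol and SAP states "For this pilot study, the requested sample size is 40". It gives the reason as "The sample size has been increased from the initial 20 to 40 to accommodate the changes in the CDS tool platform", along with a changed effort-of-breathing algorithm and the ultrasound work, and adds "We believe this sample size is necessary to test all of the stated objectives". A list by objective follows.

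- **Item 1, weaning protocol.** The plan expects a 40% success rate at the first SBT and concludes: "This means that 10-12 patients will be left to test the protocol". At 10 to 20 recommendations apiece, it counts on about 100 in total. After the first 20 patients the algorithm went from two ranges to three, and the next 20 are to show whether adherence to the revision is high.
- **Item 2, software.** The CDS tool has moved to a web browser with its rules unchanged, and the new interface is to be checked. The PRP comparison uses 10-12 weaning patients with at least 2 time points each, for more than 20 points.
- **Item 3, length of ventilation.** "approximately 20 patients should provide data to get a reliable estimate of mean and standard deviation".
- **Item 4, TPP.** "It is anticipated that 20 patients should yield a minimum of 60 TPP measurements", at an average of 3 per patient. The aim is a separation of at least 2 cmH₂O in at least 50% of observations, with a 95% confidence interval of 40-60%. The plan says this takes at least 50 observations.
- **Item 5, NIV protocol.** With 40% of extubated patients expected to go on NIV, it again arrives at 10-12 patients. Section 6 (Study Treatments) says NIV is left to the clinician and that no NIV protocol will be implemented.
- **Item 6, ultrasound.** It sets limits for bias and precision but gives no patient count.

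**The concern.** The list by objective is where the reader should learn why 40 patients are needed. For items 3 and 4 it argues from 20 instead and gives no reason for stopping there. The reader cannot tell whether those analyses use all 40 patients, the first 20 or the second 20. The same is true of the PRP comparison in item 2.

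The choice matters most for item 4, which carries the only confidence interval in the section. A proportion estimated from 50 or 60 observations is less precise than the plan says, and the decision to develop a TPP protocol is to rest on it. For item 3, the mean and SD of ventilation length feed the sample size of the later randomized trial, so the number of patients behind them, and the algorithm those patients were treated under, should be stated.

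**Working it through.** **Inputs, all from section 7:** N = 40, raised from 20; 40% pass the first SBT, so 60% enter weaning; at least 2 PRP points per weaning patient; 3 TPP measurements per patient; 40% on NIV; target interval 40-60% around 50%; stated minimum of 50 observations.

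**Step 1. Which N reproduces the plan's counts?**

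| Count | Stated | N = 20 | N = 40 |
|---|---|---|---|
| Weaning patients, 0.60 × N | 10-12 | 12 | 24 |
| PRP points, 2 × weaning patients | more than 20 | 24 | 48 |
| TPP measurements, 3 × N | at least 60 | 60 | 120 |
| NIV patients, 0.40 × N | 10-12 | 8 | 16 |

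The first three rows come from N = 20. The NIV row comes from neither: 10-12 at 40% would imply 10/0.40 = 25 to 12/0.40 = 30 extubated patients. The same 10-12 appears in item 1, where it rests on 60%, so it may have been carried over.

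**Step 2. Precision for item 4, observations taken as independent.** Half-width = 1.96 × √(0.25/n) at a proportion of 50%.

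- n = 50: ±13.9 points, or 36-64%
- n = 60: ±12.7 points, or 37-63%
- n = 120: ±8.9 points, or 41-59%
- For ±10 points: n = 1.96² × 0.25 / 0.10² = 96

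The stated minimum of 50 does not reproduce. Other interval methods do not rescue it: with 50 observations, Wilson gives 37-63% and the exact interval 36-64%. Wilson needs about 93 observations for 40-60%.

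**Step 3. Repeated measures within patient.** With 3 measurements per patient and within-patient correlation r, the half-width is multiplied by √(1 + 2r). The documents give no r, so 0.2 to 0.5 is assumed.

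- 20 patients (60 observations): ±15.0 points at r = 0.2, ±17.9 at r = 0.5
- 40 patients (120 observations): ±10.6 points at r = 0.2, ±12.7 at r = 0.5
- Largest r at which 120 observations still give ±10: 120/96 = 1.25 = 1 + 2r, so r is about 0.12

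**Step 4. Precision for item 3.** In units of the observed SD, the 95% half-width for the mean is 0.47 at n = 20 and 0.32 at n = 40. The 95% limits for the SD are 0.76 to 1.46 times the estimate at n = 20 and 0.82 to 1.28 times at n = 40. These figures assume normal data. Section 7 itself expects a wide range of durations, so they are only a guide.

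**The case against.** The strongest reply is that the study runs in two blocks and that counts built on 20 describe one block. Part of this stands.

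- **Item 1.** The text says the second 20 test the revised algorithm, and 0.60 × 20 = 12. A reader might infer that 24 should replace 10-12; the documents do not support that.
- **Item 2.** A check of the new interface can use only patients enrolled after the migration. The PRP comparison is different: no change to the PRP calculation between blocks is described, and no block is named.
- **Item 3.** The algorithm change could affect length of ventilation, so an estimate from the second 20 alone could be defended. The plan does not make that argument.
- **Item 4.** No such reason is available. Section 6 describes one TPP procedure for every enrolled patient and mentions no change between blocks.

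It can also be said that more than 20 PRP points and at least 60 TPP measurements are floors, which 40 patients would meet as well. That is correct, so the plan mostly understates its data. A reader might infer that the wording tells the analyst to discard half the patients, but nothing in the documents does so. Finally, the shortfall of 50 against 96 is an error whatever the sample size. That too is correct, and it is why naming all 40 patients is not enough and the minimum must also be restated.

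**Conclusion.** The point holds for items 3 and 4 and for the PRP comparison in item 2. Section 7 calls 40 patients necessary for all objectives but argues these parts from 20, or from a block it does not name, without saying why.

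For item 4 the consequence is a stated precision that is wrong: ±13.9 points at the stated minimum of 50 and ±12.7 at 60, against the ±10 claimed, even if observations are independent. It is tempting to conclude that 40 patients settle this. They do only if the within-patient correlation is about 0.12 or less at 3 measurements per patient. Under the assumed 0.2 to 0.5, 120 observations give ±10.6 to ±12.7.

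For item 3 the issue is an unstated choice of patients and a moderate loss of precision, not an arithmetic error. A reader might go further and read the SD limits as a firm range for the size of the later trial. They rest on normality, which the plan does not state and which a wide range of durations makes doubtful.

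The NIV count is a separate slip. It follows from neither sample size, and it concerns a protocol that section 6 says will not be implemented.

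**What to change.** In section 7, state for each item whether it uses all 40 patients or only the second 20, and restate the counts.

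- **Item 1:** no change to the 10-12 weaning patients.
- **Item 2:** base the PRP comparison on all weaning patients (about 24, at least 48 points). Keep the new-interface check to patients enrolled after the migration.
- **Item 3:** use all 40 patients, with results also shown by algorithm version.
- **Item 4:** use all 40 patients (about 120 observations). Replace the minimum of 50 with about 96 before clustering. Compute the interval with a method that allows for repeated measures within patient, and state the expected width as a range over plausible correlations.
- **Item 5:** reconcile with the statement in section 6 that no NIV protocol will be implemented, then remove or correct the count accordingly.
- **Item 6:** add the number of patients, since ultrasound is one of the reasons given for the increase.

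The cost is protocol wording and slightly more analysis, with no extra patients. If the within-patient correlation turns out to be more than about 0.12, the 40-60% interval will not be reached with 40 patients, and the plan should say so in advance.
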